## 10.4 POST-PROCEDURE

### 10.4.1 POST-PROCEDURE FOLLOW UP

- Discharge criteria decisions will be made at the discretion of the primary operator per current guidelines.
- Medication and adverse event review will be performed prior to discharge.

- Complications including vascular, stroke, heart failure, pericardial effusion, tamponade, bleeding, and death will be documented.
- The post ablation blanking period will last 3 months - any AAD is permitted but should be stopped by 4 weeks after the study procedure
- The total number of episodes of post-blanking AT or AF episode >30 seconds will be recorded
- Patients will undergo continuous 7-14 day ambulatory monitoring at 3, 6 and 12 months
- Review of medications and adverse events will be performed at the 6 and 12 month follow up

#### **10.4.2 POST-PROCEDURE MEDICATION MANAGEMENT**

- Standard cardiovascular medications are left up to the discretion of the investigator.
- Therapeutic anticoagulation beyond the requisite 2 months post-procedure time point will be at the discretion of the patient's physician.
- The post ablation blanking period will last 3 months- any AAD is permitted but should be stopped by 4 weeks after the study procedure

### **11 SAFETY**

We anticipate no significant increase in adverse events as compared to the standard AT/AF ablation procedures. The local site primary investigator will oversee the safety of the study at his/her site. As this is a mapping tool that is non-invasive we don't anticipate any adverse events unique to the case in itself. The CT scan that is required is already part of the standard of care. A detailed tally of adverse events will be kept and they are defined as such.

#### **Adverse Events**

An adverse event is any undesirable clinical occurrence in a study patient, whether or not it is related to the study intervention. Any condition that was recorded as pre-existing is *not* an adverse event unless there is a change in the nature, severity or degree of the condition.

#### **Serious Adverse Event**

Serious adverse events are defined by FDA regulation as any experience that results in a fatality or is life threatening; results in significant or persistent disability; requires or prolongs a hospitalization; results in a congenital anomaly/birth defect; or represents other significant hazards or potentially serious harm to research subjects or others, in the opinion of the investigators. Important medical events that may not result in death, be life-threatening, or require hospitalization may be considered a serious adverse event when, based upon appropriate medical judgment, they may jeopardize the patient and may require medical or surgical intervention to prevent one of the outcomes listed in this definition. Examples of such medical events include bronchospasm requiring intensive treatment in an emergency room or at home, blood dyscrasias, or convulsions that do not result in inpatient hospitalization.

#### **Unanticipated Adverse Device Effects**

An unanticipated adverse device effects (UADE) is any serious adverse effect on health or safety or any life-threatening problem caused by, or associated with, a device, if that effect, problem, or death was not

previously identified in nature, severity, or degree of incidence in the investigational plan, or any other unanticipated serious problem associated with the device that relates to the rights, safety, or welfare of subjects

### **Event Recording**

The following adverse events will be captured throughout the period of trial participation:

- Protocol-defined (as described below)
- Serious unanticipated events (serious “Other” adverse events)

### **Causality**

The investigator will assess the relationship of an adverse event to the intervention. Causality will be defined as follows:

#### *Probable*

Adverse events that, after careful medical evaluation, are considered with a high degree of certainty to be related to the ablation procedure. The following characteristics will apply:

- A reasonable temporal relationship exists between the event and the intervention, and
- The event is a known reaction to the intervention, and cannot be explained by an alternative etiology commonly occurring in the population/individual.

#### *Possible*

Adverse events that, after careful medical evaluation, do not meet the criteria for a probable relationship to the intervention, but for which a connection cannot be ruled out with certainty. The following characteristics will apply:

- The event occurs after intervention, and
- The event is not a known reaction to intervention, but cannot be explained by a commonly occurring alternative etiology

#### *Unlikely*

Adverse events that, after careful medical evaluation, do not meet the criteria for a possible or probable relationship to intervention and for which a connection is unlikely. The following characteristics will apply:

- The event does not follow a reasonable temporal sequence from administration of the intervention, or
- May have been produced by environmental factors, and there is no apparent pattern of response to the intervention.

### **Reporting of Serious Adverse Events and Unanticipated Adverse Device Effects**

All investigators must report both expected (protocol-defined) and unexpected SAEs. All protocol defined SAEs must be reported directly to the clinical center's IRB and the DCC within 5 business days of knowledge of the event, or as dictated by the specific IRB policy, whichever is sooner. All deaths, UADEs, and unexpected SAEs that are possibly or probably related to the Panoramic ECGi and Ibutilide ablation must be reported to the DCC and the clinical center's IRB within 24 hours of knowledge of the event, or as dictated by the specific IRB policy, whichever is sooner. All unexpected SAEs that are unlikely related to the study intervention must be reported to the DCC and the clinical center's IRB within 5 business days of knowledge of the event, or as dictated by the specific IRB policy, whichever is sooner.

The DCC will report these events to the DSMB chair within 72 hours of notification. All SAEs will be reported to the DSMB at least semi-annually, at the discretion of the DCC medical monitor.

### **Reporting of Unanticipated Problems**

All UPs that are also SAEs, which are at least possibly related to the study intervention, must be reported to the DCC within 24 hours of knowledge of the event. All UPs that are not SAEs must be reported to the DCC within 5 calendar days of knowledge of the event, or as dictated by the specific IRB policy, whichever is sooner.

### **DCC Reporting to FDA**

The DCC will report unexpected SAEs that are possibly or probably related to the investigational device or UADEs to FDA as appropriate. The DCC will send an initial IDE safety report communication to the FDA within 2 business days of notification from the site. The DCC will submit a follow-up safety communication to the FDA, based on source documentation or PI Report from the site, within 10 business days from notification of a UADE for this IDE trial.

### **DMC**

To meet the study's ethical responsibility to its subjects, an independent Data Monitoring Committee (DMC) will monitor results during the study. The DMC for this trial will consist of a single cardiologist who has no formal involvement or conflict of interest with the subjects, the investigators, the sponsor or the DCC. The DMC will act in a senior advisory capacity to the DCC regarding data and safety matters throughout the duration of the study. In addition, the DMC will review interim summary results of the accumulating data every 6 months or as needed. These data include adverse events (e.g., infection, bleeding, right heart failure) and mortality. They will communicate their findings directly with the DCC. The FDA will be provided a copy of any written communication from the DMC to the study sponsor related to safety concerns, or changes to the study protocol, procedures or informed consent document. The DMC will be provided a copy of any letter from the FDA to the study sponsor related to safety concerns, or changes to the study protocol, procedures or informed consent document. The clinical centers will have no contact with the DMC regarding this trial and no voting member of the committee may participate in the study as an investigator. Non-DMC members will not be allowed during DMC closed meetings. However, the PI will only be present at the open session of the meetings to clarify questions concerning the protocol and to provide updates to the DMC regarding pertinent new trial information. However, recommendations and decisions regarding the study are solely up to the discretion of the DMC.

## 12 RISKS

Patient confidentiality risks associated with any research study are minimal and include: breach of confidentiality and loss of personal data.

As the protocol includes a *standard of care* AF ablation procedure, *the risks of the procedure are generic to a standard AF ablation procedure, and include the following:*

### Potential Risks Associated with AF Ablation

- Death: End of Life
- Stroke (also called Cardiovascular Accident or CVA): may cause an interruption in the blood supply to a part of the brain
- Pericarditis: inflammation may occur in the outer lining of the heart (<1%).
- Cardiac perforation causing pleural effusion or tamponade: fluid build-up around the heart. A hole in your heart wall (*perforation*) could result in bleeding into the sac, called the pericardium, which surrounds your heart (*cardiac tamponade*). This may be treated by insertion of a needle, through your chest wall, into the sac and removal of the blood. This type of hole sometimes requires surgical repair
- Heart Valve injury (also called Valvular Damage/Insufficiency): an injury to a valve structure resulting in a loss and/or worsening of function (e.g., worsening of regurgitation score or prolapse) (<1%).
- Acute Pulmonary edema: fluid accumulation (build-up) in the lungs (<1%).
- Pulmonary embolism: blockage of a pulmonary artery; a blood clot from a vein may get stuck in the lungs. This is usually treated with drugs (<1%).
- Vascular access complications: an obstruction or perforation or damage to the vascular (blood vessel) system (2%).
- Arterial/venous thrombus: clot formation in the artery or vein (1.5%).
- AV fistula: an abnormal passageway (such as a hole) between an artery and a vein; this may allow blood to go between the arteries and veins and not through the entire body. This may cause some part of the body to not receive the usual amount of blood. This may heal on its own, but may require surgical repair (1.5%).
- Catheter insertion site hematoma: bleeding or bruising from the site of catheter placement. This may go away without treatment, but may require manual compression or surgical repair. If excessive bleeding at the site of the catheter placement continues, this could result in anemia requiring medical intervention (2%).
- Hypoxia: reduced oxygen supply to tissue (<1%).
- Infection, Localized or systemic: an infection may occur anywhere an incision or cut is made during the procedure (<1%).
- Peripheral venous thrombosis: blood clots in the vein (<1%).
- Phrenic nerve damage: damage to the nerve that controls the diaphragm and may affect your breathing. Symptoms may be temporary but in some cases can be permanent (respiratory arrest) (<1%).
- Pneumonia: infection of lungs or gathering of fluid in the lungs (<1%).
- Pseudoaneurysm: development of a false pouch in the vessel wall. This can be caused by movement of catheters in the blood vessels. This may heal on its own, but sometimes need surgical repair (<1%).
- Radiation injury resulting in dermatitis (skin burns): (<1%).
- Respiratory failure: damage to breathing that can be permanent (respiratory arrest) (<1%).

- Radiation exposure during the fluoroscopic imaging of the catheters during ablation: this may slightly increase the lifetime risk of developing a fatal malignancy or a genetic defect in offspring (<1%).
- Fluid overload: excessive fluid built up could result in pulmonary (lung) edema; congestive heart failure (CHF) may occur or may be exacerbated (worsened) due to delivery of sterile salt water (saline) during the procedure (these risks are specific to open irrigated ablation catheters) (1.5%).

#### Potential Risks Associated with Ibutilide

- Allergic reaction: Itching or hives, swelling in your face or hands, swelling or tingling in your mouth or throat, chest tightness, trouble breathing
- Arrhythmias, including Torsades de pointes
- Fast, pounding, or uneven heartbeat
- Headache
- Syncope
- Nausea
- Renal Failure

The protocol requires a CT scan to be performed. Routine CT scan with contrast is often performed if there is no contraindication as part of normal pre-procedural planning. For this protocol this will be performed on the day of the procedure. If the patient has impaired renal functions or has abnormal renal functions we will perform a non- contrast scan

## 13 STUDY MANAGEMENT

### 13.1 Study Data Collection and Processing

The Case Report Form (CRF) is an integral part of the study and subsequent reports. The CRF must be used to capture all study data recorded in the patient's medical record. The CRF must be kept current to reflect patient status during the course of the study. Patients will be identified by a 5-digit number and their initials. The investigator must keep a separate log of patient names and medical record numbers (or other personal identifiers) for their own reference. All study-related documents (CRFs, source medical records, regulatory binder) must be kept in a secure, locked environment with access limited to study personnel only.

The PI is responsible for ensuring the following: 1) adherence to the protocol; 2) verifying adherence to local regulations on the conduct of clinical research; and 3) ensuring completeness, accuracy, and consistency of the data entered in the CRF.

Final CRFs in human readable format must be reviewed and verified for accuracy by the study site Principal Investigator and signed-off. A copy of the final CRF will remain at the investigator's site at the completion of the study.

The CRF numbering convention is as follows:

01 - 2 \_ 3 \_ 4 \_ A -B -A

01 : Site # must be 2 digits (use leading zero) --- (sites 01-5)

2\_3\_4: patient screening/enrollment # (001 – 050)—must be 3 digits

**A-B-A**: Patient initials (if no middle initial, use dash)

Total 5 digits and initials for enrolled patients.

### **13.2 Confidentiality**

Patient information will be kept confidential and managed according to the 1996 HIPAA guidelines. Each patient will be given a unique subject number and will be identified by this number and their initials. All data used in the analysis and reporting of this evaluation will be without identifiable reference to the patient. Data relating to the study might be made available to third parties (for example in case of an audit performed by regulatory authorities) provided the data are treated confidential and that the patient's privacy is protected.

### **13.3 Deviations from Protocol**

The investigator will not deviate from the protocol except in medical emergencies or in unforeseen, isolated instances where minor changes are made that will not increase the patient's risk or affect the validity of the trial. In medical emergencies, prior approval for protocol deviations will not be required, but the IRB/EC must be notified within five days of the incident.

### **13.4 Role of the Coordinating Center**

As principal investigator and study sponsor of this clinical study, [name] assumes the overall responsibility for the conduct of the study, including assurance that the study meets national and institutional guidelines for study conduct. In this study, [name] will have certain direct responsibilities and will delegate other responsibilities to his staff at the Coordinating Center, the Icahn School of Medicine at Mount Sinai. The coordinating center will: 1) ensure adherence to the national and institutional regulations; 2) develop and distribute protocols and case report forms; 3) coordinate data organization; 4) perform statistical analyses; 5.) provide on-site and remote monitoring.

### **13.5 Withdrawal of Subjects**

A subject may withdraw from the study at any time should they choose to do so. Additionally, subjects may be withdrawn by the investigator if deemed appropriate due to safety or compliance issues.

### **13.6 Economic Impact on Subjects**

There are no additional costs related to involvement in this study. Since the cost of the procedure will be included within the Disease Related Group (DRG) charge, neither patient nor insurance provider will incur additional cost.

## **14 ETHICAL AND REGULATORY CONSIDERATIONS**

### **14.1 Maintaining Records (21 CFR 812. 140 (B))**

All clinical sites will maintain study records for two years after research termination. The Coordinating center will maintain copies of correspondence, data, shipment of devices, adverse device effects and other records related to the clinical trial.

## **14.2 Institutional Review Board (IRB) / Ethics Committee (EC) Information**

This protocol and the informed consent must be reviewed and approved by the appropriate IRB/EC where the trial is to be conducted before enrollment of patients. Changes to the protocol that may increase the risk or present new risks to the patient, or may adversely affect the validity of the trial, must be approved in writing by the IRB/EC before the change is made.

The study site Principal Investigator(s) is responsible for submitting and obtaining initial and continuing review (at intervals not greater than once a year) of the trial by their IRB/EC.

## **15 CLINICAL CENTERS**

The study will be conducted in up to 4 sites in the United States and 1 in Europe. Each clinical center will be required to obtain IRB/EC approval for the protocol and consent (and their revisions) in a timely fashion, to recruit patients, to collect data and enter it accurately in the electronic data capture (EDC) system, to faithfully follow the protocol and adhere to the standards of Good Clinical Practice (GCP). In addition, centers will be required to provide the DCC with the information necessary for interim, annual, and final reports, to provide source documents, data and regulatory documents for study monitors, provide prompt responses to DCC inquiries, and to participate in analyses and reporting of study results.

### **Investigator Profile**

All cardiologists, coordinators and other investigators in the study must complete the Investigator Profile form, including hospital affiliation, address, telephone, fax, beeper and email information. The cardiologist and coordinator must email or fax their CV, Conflict of Interest Statement and Financial Disclosure Certification, and Institutional Health Insurance Portability and Accountability Act (HIPAA) Certificates to the DCC.

### **Qualifications and Training**

Clinical investigators will be electrophysiologists with expertise in AF ablation. The certified operator will either perform the ablation on their own patient, or participate in the ablation of an enrolled patient. The clinical site Principal Investigator will be responsible for overseeing the ongoing performance of the other participating investigators at that site over the course of the study.

All clinical site investigators and coordinators will be trained by the DCC in the specifics of the protocol at a site initiation visit in advance of patient enrollment. In addition, the investigators and coordinators will undergo a separate training session to gain familiarity with the electronic data capture system.

## **16 DATA HANDLING**

Information about patients will be kept confidential and managed according to the requirements of the United States of American Health Insurance Portability and Accountability Act of 1996 (HIPAA). Those regulations require a signed patient authorization informing the patient of the following:

1. What protected health information (PHI) will be collected from patients.
2. Who will have access to that information and why.
3. Who will use or disclose that information.
4. The rights of a research patient to revoke their authorization for use of their PHI.

In order to ensure patient confidentiality, all case report forms and patient information (CT / MRI, if reviewed), fluoroscopic and endoscopic images, ECGs) will be de-identified and replaced with a unique patient identifier. Information will be stored in the office of the local study coordinator, which will be kept in a secure, locked location. The research study coordinators, principal investigator and co-investigators will be the only personnel with access to this data. All data will be stored without any patient information apart from the unique three digit patient identifier. Electronic data will be encrypted and password-protected.

## 17 DATA ANALYSIS

Baseline clinical characteristics (e.g. age, gender, renal function) and procedural characteristics (e.g. surface intracardiac electrogram, and imaging findings) of the patients will be collected and analyzed. All continuous variables will be performed as the mean  $\pm$  standard deviation, and all categorical variables as a percentage of the total study population.

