## PROTOCOL SUMMARY

Title:	Panoramic ECGi to guide Ablation of Non-Paroxysmal AF: Effect of Ibutilide on AF Source Location and Organization
Objective:	This prospective, multicenter observational study will examine the 1) Effect of Ibutilide on the number and size of the driver domains 2) Effect of ablation of Ibutilide-organized driver domains 3) Effect of PV isolation on driver domains
Design:	This is a prospective, multi-center, non-randomized, un-blinded, observational trial.
Enrollment:	
Eligible subjects will be consented for participation in the trial prior to undergoing AF ablation. Patients are considered eligible if they have
 
 
1. <math>\geq 18</math> years of age.
 
2.           
 
1) Symptomatic persistent AF refractory or intolerant to at least 1 class I or III antiarrhythmic medication Persistent AF - defined as Persistent: AF that is sustained <math>> 7</math> days. Episodes of AF which are terminated by electrical or pharmacologic cardioversion after <math>\geq 48</math> hours of AF, but prior to 7 days, should also be classified as persistent AF episodes.
 
2) Planned to undergo first catheter ablation procedure ( prior atrial flutter typical is allowed)
 
 
 
3. Ability to understand the requirements of the study and sign the informed consent form.
 
4. Willingness to adhere to study restrictions and comply with all post-procedural follow-up requirements
 
5. Projected lifespan greater than 1 year.
 
 
Patients will be excluded from the trial if:
 
 
1. They have baseline prolonged QT or renal failure precluding safe use of ibutilide
 
2. Rheumatic heart disease,
 
3. Current intra-cardiac thrombus,
 
4. History of MI or CABG within 6 weeks;
 
5. Class IV HF,
 
6. Unable to sign consent
 
7. Projected lifespan of <math>< 1</math> year
 
8. Women known to be pregnant or to have positive beta-HCG.
 
9. Participation in another study that would interfere with this study.
 
10. Unstable Angina
 
11. Recent cerebral ischemic events
 
12. Contraindication to anticoagulation
 
13. Prior history of polymorphic ventricular tachycardia or torsades de pointes
 
 
Patients are considered enrolled once consented. Patients who do not

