## 2 STUDY OBJECTIVE

This prospective, multicenter observational study will examine the ability of ECGi mapping to

- 1) Effect of Ibutilide on the number and size of the driver domains
- 2) Effect of ablation of Ibutilide-organized driver domains
- 3) Effect of PV isolation on driver domains

We hypothesize that this approach will lead to successful arrhythmia control

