## 3 INTRODUCTION, RATIONALE

Beyond PV isolation, ablation strategies for non-paroxysmal AF remain controversial although several types of targets have been proposed: non-PV triggers, continuous fragmented atrial electrograms, ganglionated plexi, and linear lesions. In STAR AF-2, PV isolation (PVI) alone resulted in successful maintenance of SR in only 59% of patients with persistent AF. This clearly reveals the need for establishing strategies to address non-PV sources of AF in non-paroxysmal AF. However, in the STAR AF-2 trial, after 18 months, the freedom from recurrent AF in patients assigned to PVI alone (59%) was not improved by the addition of either CFAE ablation (49%) or linear ablation (46%),  $p=0.15$ . Thus, beyond PV isolation, there is little consensus as to what additional lesion sets one should perform.

Localized driver domains perpetuating AF have been difficult to detect with conventional techniques because of the limits of sequential temporospatial mapping, intermittent firing, and, presumably, spatial meandering of rotor-like activity. However, panoramic biatrial AF mapping using a body surface array with 252 electrodes has been used to enable activation and phase-based analysis of body surface potentials. This noninvasive “ECG imaging”(ECGi) approach has been reported able to identify driver domains that, when targeted for ablation (along with PVI), can terminate AF. And most recently, the non-

randomized prospective multicenter AFACART study (8 centers, 118 patients) revealed that for persistent AF, the combination of PVI and ablation of driver domains identified by ECGi resulted in i) acute AF termination in 66% of patients, and ii) one-year freedom from recurrent atrial arrhythmias in 83%.

The efficacy of an ablation strategy of targeting these driver domains will require a number of clinical studies: both large randomized studies and smaller mechanistic studies. To this latter point, we propose conducting an exploratory study of the use of panoramic ECGi in non-paroxysmal patients, in which the effect of pharmacological organization of driver domains will be evaluated, by the administration of progressive doses of Ibutilide.

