## **8 SAMPLE SIZE**

[figure not shown]
This safety and efficacy study will enroll 20 patients across 1US centers and 1 OUS center. This number has been determined on the basis of study feasibility and not by statistical means. This is a feasibility study of the mapping system (ECGi) performance in which the sample size of the clinical investigation is intended to provide preliminary estimates of safety and performance.

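### Section 8 promises preliminary estimates of safety and performance from 20 patients, but Section 17 reports only percentages and mean ± SD, with no measure of precision for any endpoint

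*Combined protocol and SAP*

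**What the plan says.** Section 8 states "This safety and efficacy study will enroll 20 patients across 1US centers and 1 OUS center". On the size it says "This number has been determined on the basis of study feasibility and not by statistical means", and it gives the purpose of that size as "intended to provide preliminary estimates of safety and performance". Section 2 adds one directional sentence, "We hypothesize that this approach will lead to successful arrhythmia control", with no threshold.

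Section 6.1 lists two primary endpoints: the acute procedural outcome, and freedom from recurrent AT/AF at 12 months. The additional endpoints include the effect of PV isolation on driver domains, the number and size of drivers, the percentage reduction in driver regions after ibutilide, AF termination and post-ablation inducibility.

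The only analysis text is Section 17. It names baseline and procedural characteristics, then gives two general rules: mean ± standard deviation for continuous variables, and "all categorical variables as a percentage of the total study population". It does not name the 12-month endpoint or adverse events. The Protocol Summary enters N/A for both the primary and the secondary analysis.

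**The concern.** A study justified by estimation should report how precise its estimates are. Followed literally, Section 17 would give the 12-month result as a bare percentage and a complication that did not occur as 0%. With about 20 patients both look firmer than they are. Safety is the sharper case, because Section 11 already expects no significant increase in adverse events over standard ablation, and a bare 0% would seem to confirm it.

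The mechanistic endpoints have a related problem. A standard deviation describes the spread between patients. It does not say how well the mean change in driver number or size has been estimated.

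**Working it through.** **Inputs.** n = 20 (Section 8). The plan states no confidence level, precision target or dropout rate. I assume two-sided 95% intervals and, to begin with, 20 evaluable patients. There is no sample-size calculation to reproduce.

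**1. Binary outcomes.** The Clopper-Pearson limits for x events in n are the 2.5% quantile of Beta(x, n − x + 1) and the 97.5% quantile of Beta(x + 1, n − x).

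| Observed | Percentage | Exact 95% CI |
|---|---|---|
| 12/20 | 60% | 36.1–80.9% |
| 16/20 | 80% | 56.3–94.3% |
| 17/20 | 85% | 62.1–96.8% |
| 1/20 | 5% | 0.1–24.9% |
| 0/20 | 0% | 0–16.8% |

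For zero events the upper limit is 1 − 0.025^(1/n). At n = 20 this is 16.8%; the one-sided 95% bound, 1 − 0.05^(1/20), is 13.9%. The Wilson interval for 16/20, 58.4–91.9%, reads the same way.

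**2. What a 0% would mean.** Section 12 quotes 2% for vascular access complications and for insertion-site hematoma. At a true risk of 2%, the chance of no event in 20 patients is 0.98^20 = 0.67. Zero events is therefore the likely result for a complication of that frequency, and says little about whether its risk has risen.

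**3. Fewer than 20 evaluable.** Under Section 9, patients count as enrolled at consent, become screen failures if not ablated within 90 days, and may withdraw. Under Section 10.3, ibutilide and the maps that follow it apply only if AF persists after PV isolation, and drivers are ablated only if AF then still continues. The documents do not say how many patients will reach each step, so these counts are illustrations:

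- At the same 80%, 8/10 gives 44.4–97.5%, a width of 53.1 points, against 38.0 points for 16/20.
- 15/18 (83.3%) gives 58.6–96.4%, a width of 37.8 points, against 34.7 points for 17/20 (85%).
- Zero events: 0/16 allows up to 20.6%, and 0/12 up to 1 − 0.025^(1/12) = 26.5%.

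The denominator matters in itself. If 12 patients received ibutilide and none had torsades de pointes, the relevant limit is 26.5%. Dividing by a total study population of 20 would imply 16.8%.

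**4. Continuous outcomes.** The 95% half-width for a mean is t(0.975, 19)/√20 = 2.093/4.472 = 0.47 SD. For a before-after change, the SD needed is that of the within-patient differences. If both time points have SD s and correlation r, it is s√(2(1 − r)). The documents give no r. For r = 0, 0.5 and 0.8 (assumed), the half-width is 0.66s, 0.47s and 0.30s. Mean ± SD at each time point therefore does not determine the precision of the change.

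**The case against.** The strongest reply is that this is openly a feasibility study. Section 3 calls it exploratory and Section 8 already calls its estimates preliminary. A reader given a percentage and n can compute an exact interval, and a mean, SD and n yield a t-interval. If the percentage reduction after ibutilide is calculated per patient, its mean ± SD suffices too.

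Much of this stands. Sizing on feasibility is not an error, and intervals added at the reporting stage would introduce no bias. The reply fails in three places: the 12-month outcome if patients are lost before then, before-after changes reported only as separate summaries, and any endpoint whose evaluable number differs from the total study population.

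A reader might also infer that the study will declare arrhythmia control from a point estimate. The documents do not support that. Section 2 offers a hypothesis without a threshold, the Summary lists no formal analysis, and there is no test or success rule.

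A second tempting inference is that 20 patients cannot separate the 59% and 83% success rates in Section 3. The interval for 16/20 does contain both. But the plan cites those rates as background and not as benchmarks, and they refer to different follow-up times (18 months and one year).

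**Conclusion.** The point holds as a gap in reporting. The stated purpose is estimation, and the stated method gives no precision for any endpoint. With 20 evaluable patients the unreported uncertainty is roughly −24 to +14 percentage points around an observed 80% (80 − 56.3 = 23.7; 94.3 − 80 = 14.3), and up to 16.8% behind an observed 0%. At a given observed percentage it grows as the evaluable number falls.

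These figures rest on two-sided 95% exact intervals and on illustrative counts, since the plan does not give evaluable numbers. The conclusion is not a criticism of n = 20, and does not imply that the plan would claim efficacy. It is a worthwhile, low-cost improvement.

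**What to change.** Amend Section 17 to commit to the following:

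- Exact (Clopper-Pearson) 95% intervals for AF termination, post-ablation inducibility and each complication, including those with zero events.
- A Kaplan-Meier estimate of 12-month freedom from AT/AF with a 95% interval. Note that recurrence times are known only roughly, because Section 10.4.1 schedules 7–14 days of monitoring at 3, 6 and 12 months. State that the estimate is read after the 12-month recording is complete.
- Within-patient mean changes in driver number and size, with 95% intervals from the paired differences.
- The number evaluable for each endpoint, in place of a single total-population denominator, since post-ibutilide maps and driver ablation exist only for patients who remain in AF after PV isolation.

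The cost is a short amendment and minutes of analysis, with no new patients, visits or data. The one drawback is that the reported figures will look less certain, which is accurate at this sample size.
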